2. OBJECTIVES

PRIMARY OBJECTIVES: The primary study goal is to document the efficacy of the CyberKnife procedure, where efficacy is defined by biochemical Disease-Free Survival (bDFS), using Phoenix and ASTRO definitions, at 5 years. This will be accomplished through testing the primary efficacy hypotheses detailed in Sections 1.1.5 and 11.2. Additionally, descriptive statistics will be provided comparing the CyberKnife SRS bDFS rate to published HDR monotherapy bDFS rates reported in the literature. A second primary study goal is to accurately measure the rates of acute and late grade 3-5 gastrointestinal and genitourinary toxicity observed during the five years following CyberKnife SRS for prostate cancer.

SECONDARY OBJECTIVES: to measure the following in the study population: Rates of local failure, distant failure, clinical disease-free survival, disease-specific survival, and overall survival; quality of life (QOL) in generic and organ-specific domains; work effort required in treatment planning and delivery of CyberKnife SRS.

Patients will be followed annually to 10 years, to collect additional data for descriptive analysis.

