- 1.14. Another potential benefit of CyberKnife radiosurgery relative to HDR brachytherapy is better preservation of potency, even if the radiation distribution is essentially identical between these modalities. This is so because needle trauma has been identified as a potentially significant contributory factor to erectile dysfunction with brachytherapy, including HDR-based monotherapy technique, presumably due to direct physical injury to the neurovascular bundle and/or bulb of the penis, particularly when greater than 13 needle insertions are performed.¹⁵ By comparison, CyberKnife radiosurgery is noninvasive, and so removes this particular erectile dysfunction risk factor.
- 1.15. To confirm our hypothesis that CyberKnife radiosurgery may be made to resemble a "noninvasive HDR dosimetry delivery system," in addition to simply creating equivalent dosimetry, it is necessary to show clinical equivalence both in terms of efficacy and toxicity.

Table 1. 5-Year bDFS Outcomes for HDR-Monotherapy for Prostate Cancer

HDR Details	Institution	# pts	Medianf/u yrs	Phoenix	ASTRO
6-7.25 Gy x 6	CA Endocurie ¹⁸	117	3.3		97%
9.5 Gy x 4	Beaumont ¹⁹	95	4.2		98%
7.5 Gy x 6	Texas Tech ²⁰	145	5		90%
6.5 Gy x 6	Gamma West – Fav. (SLC) ²¹	209	1.2	96%*	99%*
	Gamma West – Int. 21	119	1.2	89%*	89%*
6 Gy x 8-9	Osaka (Japan) ²²	111	2.25		70%†
	Totals	796	2.4		90%

^{*3} year result; Projecting constant failure rate in this series to 5 years yields 98% and 82% ASTROdefinition PSA DFS for favorable and intermediate risk cases, respectively. †Predominantly unfavorable prognosis cases in this series; 5 year local control is 97%.

Based on the data provided in the reports summarized above, and adding a PSA DFS degradation factor to the Gamma West series to compensate for their short median follow-up, the average calculated 5 year HDR monotherapy ASTRO-based PSA DFS is 98% for favorable prognosis, 82% for intermediate prognosis and 59% for unfavorable prognosis cases. There are too few Phoenix-based PSA DFS results to project a meaningful Phoenix-based HDR monotherapy PSA DFS efficacy result.

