9.3. QUALITY OF LIFE ASSESSMENTS

- 9.3.1. SF-12: The SHORT FORM-12 Health Survey measures generic health status relevant across different age, disease, and treatment groups. It provides a comprehensive, psychometrically sound assessment of health status from the patient's point of view by scoring responses to standard questions. The SF-12 is self-administered, and can usually be completed in less than 3 minutes without assistance.
- 9.3.2. EXPANDED PROSTATE CANCER INDEX COMPOSITE (EPIC)-26: is a validated comprehensive instrument developed to assess patient function and bother after prostate cancer treatment. It was developed by an expert panel of urological oncologists, radiation oncologists (including those with brachytherapy expertise), survey researchers, and prostate cancer nurses, to address symptoms related to radical prostatectomy, external beam radiotherapy, prostate brachytherapy, and hormonal symptoms. See appendix VI.
- 9.3.3. AMERICAN UROLOGICAL ASSOCIATION (AUA) SYMPTOM INDEX: Also known as the International Prostate Symptom Score (IPSS), this widely used index assesses urinary symptom bother. See appendix VI.
- 9.3.4. SEXUAL HEALTH INVENTORY FOR MEN (SHIM): is a widely used, internationally validated and sensitive instrument for assessing erectile dysfunction¹.
- 9.3.5. UTILIZATION OF SEXUAL MEDICATIONS/DEVISES: provides context for interpreting the sexual domain score of the EPIC questionnaire.
- 9.4. CRITERIA FOR DISEASE CONTROL: intervals will be measured from enrollment date.
 - 9.4.1. BIOCHEMICIAL DISEASE-FREE SURVIVAL (bDFS): is measured as time to PSA failure. While earlier reports of prostate cancer patients treated with radiotherapy have used the ASTRO consensus definition (ACD) of PSA failure, recent studies^{2,3,4} have suggested the "nadir+2" definition is a more sensitive and specific definition of biochemical failure. Indeed, a recent expert panel met in Phoenix⁵ and developed a consensus recommendation using the later definition. So that comparisons can be made with earlier literature, both definitions shall be used:

П

- 9.4.1.1.Phoenix definition: failure occurs when the PSA is 2 ng/ml more than the lowest PSA measurement before the current one, with no backdating. Administration of salvage therapy (hormones, surgery, etc...) will be considered failure.

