11. STATISTICAL CONSIDERATIONS

- 11.1. OVERVIEW: The study's primary goals are to determine CyberKnife monotherapy efficacy and to evaluate the incidence of grade 3 or higher toxicity as stated in Section 2.0. Per RTOG/ECOG, acute toxicity will be defined as occurring within 90 days from completion of treatment. Late toxicity will be defined as occurring more than 90 days from completion of treatment. It is graded based upon Common Terminology Criteria for Adverse Events (CTCAE), v3.0., and RTOG/ECOG definitions (see appendix 5).
- 11.2. INTERIM ANALYSIS: An interim analysis was performed. The results below are based on an overall one-sided alpha of 0.05 and using the O'Brien-Fleming spendingfunction, and were calculated using nTerim (Statistical Solutions Ltd). The interim analysis is based on 4,512 months of follow-up, out of a total possible of 15,600 months (60 months* 260 Subjects). Hence the interim analysis is performed with approximately 29% of the total data possible for the final analysis. The final alpha must now be 0.04999. If the Z-score at the interim analysis exceeds 3.45701, then the trial could be stopped. If th Z-score doesn't exceed 3.45701, then the trial will continue through the primary assessment period of 5 years, where the P-value for success is at most .0499991.

	Look 1	Final Analysis- Look 2
proportion of information	0.29	1.0
Z-Score Boudary	3.45701	1.64575
Nominal Alpha	0.00027	0.049991
Incremental Alpha	0.00027	0.05

11.3. SAMPLE SIZE:

Primary Efficacy Endpoint and Hypothesis: 5-Year Biochemical Disease-Free Survival(bDFS) Among CyberKnife Treated Patients

bDFS is the primary efficacy outcome for the study. The proportion of patients disease-free within 5 years of the initial procedure is the rate of interest. The null and alternative hypotheses are as follows:

$$H_0: \pi < 90\%$$

 $H_1: \pi \ge 90\%$

 π • • is the expected proportion of CyberKnife treated patients bDFS at 5 years. The CyberKnife procedure is considered to be effective if this study's result verifies that the lower limit of the one-sided 95% confidence interval for π is not below 90%. Statistical Sample Size Derivation

Primary Efficacy Objective

We calculate the CyberKnife Treatment Group sample size, N, required to test the null hypothesis that the rate in the Treatment Group is less than 90%, against the one-sided alternative hypothesis that the rate is at least 90%...

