We chose N large enough to test the null hypothesis against the alternative hypothesis with power equal to 80% at the one-sided 5% significance level.

Let Z_u denote the upper u-th percentile of the standard normal distribution. Hence $Z_{.05} = 1.645$ corresponding to the one-sided 5% level of significance and $Z_{.20} = 0.84$ corresponds to 80% power. Then the sample size is determined by Formula 1:

$$N = \frac{\left[z_{\beta}\sqrt{\pi_{1}(1-\pi_{1})} + z_{\alpha}\sqrt{\pi_{0}(1-\pi_{0})}\right]^{2}}{\left[\pi_{1} - \pi_{0}\right]^{2}}, \text{ where}$$

 π_1 is the expected proportion of CyberKnife treated patients bDFS at 5 years if the alternative hypothesis is true; the bDFS rate is then expected to equal or exceed 0.94. For purposes of sample size estimation, we require 80% power if $\pi_1 \geq 0.945$. π_0 is the expected lower limit of the 95% confidence interval for π and is set equal to 0.90. Then N= 232. Allowing 8% sample size degradation for lost to follow-up, the sample size must be increased to 232/.92 = 253 subjects.

Primary Safety Objective

The primary safety objective is to establish with 95% confidence that the percentage of CyberKnife treated patients experiencing \geq Grade 3 toxicity is not more than 5% higher than the approximately 9% 5-year rate extrapolated from Table 2, Section 1.15.

With N=232 CyberKnife treated subjects, if the observed \geq Grade 3 toxicity rate equals 9%, then with 95% confidence the "true" rate \leq 12.6%. Since the difference between 12.6% and 9% is less than 5%, the sample size of 232 subjects is more than large enough to meet the primary safety objective.

11.3.1 ACCRUAL RATE: the initial three months while institutions are obtaining IRB approval, therefore we do not expect to meet the targeted monthly accrual rate until after the first three months. The estimated accrual rate is 2 patients per study site per month. Expectations of 5 treating study sites assumes an accrual period of approximately 29 months total.

11.4STATISTICAL METHODS

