11.4.1 PRIMARY OBJECTIVES

1. Efficacy

The lower limit of a one-sided 95% confidence interval for the expected proportion of patients experiencing biochemical disease-free survival (bDFS) is estimated by L, where

$$L = \frac{(2np + Z_{0.05}^2) - Z_{0.05}\sqrt{Z_{0.05}^2 + 4pn(1-p)}}{2(n + Z_{0.05}^2)}$$

Here "p" is the observed proportion of patients experiencing bDFS in either arm of the trial. The CyberKnife intervention will be considered to be effective if this study's result verifies that L is not below 90%.

2. Safety

The upper limit of a one-sided 95% confidence interval for the expected proportion of patients experiencing \geq Grade 3 gastrointestinal and genitourinary toxicity is estimated by U, where

$$U = \frac{(2np + Z_{0.05}^2) + Z_{0.05}\sqrt{Z_{0.05}^2 + 4pn(1-p)}}{2(n + Z_{0.05}^2)}$$

Here "p" is the observed proportion of patients experiencing ≥ Grade 3 gastrointestinal or genitourinary toxicity. The CyberKnife intervention will be considered to be safe if this study's result verifies that U is not more than 5% higher than the literature rate of 9%...

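### The primary 5-year bDFS test does not say whether the Phoenix or the ASTRO definition decides, and the planning rate behind its power is ASTRO-only

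*Combined protocol and SAP*

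**What the plan says.** Section 2 sets the primary goal: "efficacy is defined by biochemical Disease-Free Survival (bDFS), using Phoenix and ASTRO definitions, at 5 years". Section 9.4.1 describes nadir+2 as the more sensitive and specific definition and as the newer consensus recommendation, then keeps both: "So that comparisons can be made with earlier literature, both definitions shall be used". The two rules differ. Phoenix counts a rise of 2 ng/ml over the lowest earlier PSA, without backdating. ASTRO needs three consecutive rises, dates failure to a midpoint, and forgives early rises that are followed by a decline not caused by hormones.

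Section 11.3 has one rate: "The proportion of patients disease-free within 5 years of the initial procedure is the rate of interest". The null is below 90% and the alternative is 90% or more. N is chosen "with power equal to 80% at the one-sided 5% significance level". The null value "and is set equal to 0.90", without a source. On the alternative: "For purposes of sample size estimation, we require 80% power if" the true rate is at least 0.945. In Section 11.4.1 a single lower limit L is computed from one p, which "is the observed proportion of patients experiencing bDFS in either arm of the trial". None of these places names a PSA-failure definition. The interim boundary in Section 11.2 is also given for a single, unspecified Z-score.

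Section 1.15 labels the 98% (favorable) and 82% (intermediate) 5-year rates as ASTRO-based and adds: "There are too few Phoenix-based PSA DFS results to project a meaningful Phoenix-based HDR monotherapy PSA DFS efficacy result". The 94% predicted rate for a 70/30 case mix follows from those two figures.

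**The concern.** A patient can fail under one definition and not the other. In the favorable group of the only series in Table 1 that reports both, 3-year control is 96% by Phoenix and 99% by ASTRO. With one test and two candidate endpoints, three readings are open: either suffices, both are needed, or one decides. The first two carry operating characteristics other than those stated, and the third needs a choice that the plan does not make. If the choice is left until 5-year results are known, the success claim can depend on it. Section 2 does not settle the matter: it refers to hypotheses in Sections 1.1.5 and 11.2, and the current 11.2 is the interim analysis.

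Power is a second matter. It was planned from ASTRO rates, so a reader cannot tell what power a Phoenix-based test would have.

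**Working it through.** **Inputs.** Section 11.3: null 0.90, alternative 0.945, one-sided alpha 0.05, power 80%, loss 8%. Section 1.15: case mix 70% low / 30% intermediate; planning rates 98% and 82% (ASTRO); one series with 3-year Phoenix 96% and 89% and ASTRO 99% and 89% (209 favorable and 119 intermediate patients, median follow-up 1.2 years). The correlations between the two tests below are assumptions; the documents give none.

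**1. The plan's sample size reproduces.** Formula 1:

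N = [0.84·√(0.945·0.055) + 1.645·√(0.90·0.10)]² / 0.045² = 231.7, so 232; 232/0.92 = 252.2, so 253.

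Under the rule L ≥ 0.90, success needs at least 217 of 232 (L = 0.9034; 216 gives 0.8984). The exact size is 4.0% and the exact power at 0.945 is 79.0%. With all 253 evaluable, 236 are needed (size 4.5%, power 83.9%).

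**2. If either definition may pass**, with both true rates at 90% and a nominal 5% for each test:

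| Correlation | P(at least one passes) |
|---|---|
| 0 | 1 − 0.95² = 9.75% |
| 0.7 | 8.0% |
| 0.9 | 6.8% |

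The last two rows come from a bivariate normal with cut-off 1.645. Because the discrete rule is slightly conservative, starting from its exact 4.0% size at n = 232 gives 1 − 0.96² = 7.8% under independence.

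**3. If both must pass**, each with 80% power:

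| Correlation | Joint power |
|---|---|
| 0 | 0.80² = 64% |
| 0.7 | 71% |
| 0.9 | 75% |

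Type I error is not inflated on this reading.

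**4. If ASTRO alone decides**, step 1 applies unchanged: the stated alpha and the power at 0.945 stand.

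**5. Illustration of a Phoenix rate.** The plan carries 3-year rates to 5 years with a constant failure rate, S(5) = S(3)^(5/3). On the ASTRO column this gives 0.99^(5/3) = 98.3% and 0.89^(5/3) = 82.3%, matching its 98% and 82%. On the Phoenix column:

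- favorable 0.96^(5/3) = 93.4%
- intermediate 0.89^(5/3) = 82.3%
- 70/30 mix: 0.7·0.934 + 0.3·0.823 = 90.1%

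Approximate sampling error, treating the 3-year rates as simple binomial proportions with complete 3-year follow-up and using the delta method:

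- favorable SE = (5/3)·0.96^(2/3)·√(0.96·0.04/209) = 0.0220
- intermediate SE = (5/3)·0.89^(2/3)·√(0.89·0.11/119) = 0.0442
- mix SE = √[(0.7·0.0220)² + (0.3·0.0442)²] = 0.0203
- approximate 95% range: 90.1% ± 1.96·2.03 points = 86.1% to 94.1%

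A low-risk share of 60% to 80% moves the point value between 89.0% and 91.2%.

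Exact probability of at least 217 of 232:

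| Basis | True rate | P(success) |
|---|---|---|
| Phoenix, lower end | 86.1% | under 0.1% |
| Phoenix, point value | 90.1% | 4.4% |
| Phoenix, upper end | 94.1% | about 70% |
| ASTRO, same method and series | 93.5% | 56% to 57% |
| Planning alternative | 94.5% | 79.0% |

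The ASTRO mix is 0.7·0.983 + 0.3·0.823 = 93.5%. With the plan's rounded inputs it is 0.7·98% + 0.3·82% = 93.2%, for which P(success) is 48.6%.

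**The case against.** The strongest defence is that Section 9.4.1 gives the definitions roles: nadir+2 is presented as the better definition, and both are kept for comparison with earlier literature. That explains why both are reported. It does not say which carries the success claim, and it sits awkwardly with planning rates that are all ASTRO-based.

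It is also fair that both definitions use the same PSA series, so the tests should be strongly correlated and the independence figures are outer values. At a correlation of 0.9 the effects are modest. If all 253 patients were evaluable, with 83.9% power for each test, the same bivariate normal calculation gives joint power of about 79.5%. This limits the size of the problem but leaves the decision rule undefined.

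Three stronger readings are tempting, and the documents do not support them.

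- A reader might infer that the 90% null was taken from ASTRO data. It equals the ASTRO total in Table 1, but Section 11.3 gives no derivation, and that total includes a series of mainly unfavorable cases. The match does not show origin.
- A reader might infer that the plan itself puts the Phoenix rate at the null. It does not; it declines to project one. The 90.1% is this review's extrapolation from one short series, with a range that reaches the planning region.
- A reader might infer that every reading breaks a stated property. That is untrue if ASTRO alone decides, and type I error is preserved if both must pass.

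The ASTRO shortfall against 80% in the last table is a separate matter: it comes from planning at 0.945 when the inputs give 93% to 94%, not from having two definitions.

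**Conclusion.** The point holds in this form: the plan has two primary definitions, one test and no deciding rule. Allowing either to pass gives a nominal error of about 6.8% at a correlation of 0.9, and 9.75% under independence. Requiring both gives about 75% or 64% joint power when each test has 80%. These sizes depend on the assumed correlation. The direction does not, for any imperfect correlation with both true rates at the null (error) or both tests at 80% (power).

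The stated power has no Phoenix basis, because the 98%, 82% and 94% figures are ASTRO-only. The source of the 90% null is simply not given. The Phoenix illustration (about 90.1%, roughly 86% to 94%; success probability about 4%, from under 0.1% to about 70%) shows only that the choice of definition could decide the result. It is not an estimate of the trial's prospects. The ambiguity should be resolved before the 5-year analysis.

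**What to change.** In Sections 2, 11.3 and 11.4.1, name one definition as deciding, and state that the same one applies to the interim and final tests. Report the other as supportive, without a success claim of its own. Do this before the 5-year analysis.

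- If ASTRO decides: keep the 90% null and describe the power as ASTRO-based.
- If Phoenix decides: state that the 0.945 planning rate and the 80% power were not derived for Phoenix, and show power over a range of assumed Phoenix rates. Keep the 90% null, because Section 11.2 reports that an interim analysis has already been performed and the null should not be reset after a look at the data.

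The cost is a few sentences, plus a short power table if Phoenix is chosen. The sponsor gives up the option of claiming success on whichever definition turns out more favourable.

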3. DEVICE

Accuray, Inc. (Sunnyvale, CA), received FDA clearance in July 1999 to provide treatment planning and image guided stereotactic radiosurgery and precision radiotherapy for lesions, tumors and conditions of the brain, base of skull and cervico-thoracic spine, head and neck using the CyberKnife. On August 10, 2001, Accuray, Inc. received 510(k) FDA clearance (510(k) number K011024) to provide treatment planning and image-guided stereotactic radiosurgery and precision radiotherapy for lesions, tumors, and conditions anywhere in the body when radiation treatment is indicated.

4. PRETREATMENT EVALUATION

- 4.1. Complete history and physical exam
- 4.2. DRE findings
- 4.3. Assessment of performance status
- 4.4. Histological evaluation of prostate biopsy with assignment of Gleason score
- 4.5. Evaluation of the pelvic lymph nodes with CT or MRI is optional
- 4.6. Serum PSA. Laboratory evaluation must be done within 90 days prior to registration, or <60 days prior to hormone therapy, and 30 or 90 days after discontinuing finasteride or dutasteride, respectively.
- 4.7. CBC, platelets, serum BUN, creatinine and testosterone; may be drawn after registration
- 4.8. Transrectal ultrasound volume study of the prostate or a digital rectal exam (DRE) will be performed prior to enrollment to verify the prostate volume. The prostate volume may be obtained by step section summated measurements at 5 mm intervals through the entire gland (stepping method) or the by the length-width-height method. An MRI-based prostate volume measurement will also be acceptable (specify which modality).
 - 4.8.1. Measurement from CT or ultrasound 6 months prior to registration, or 14 days prior to registration if hormone therapy given; if patient had taken finasteride or dutasteride, volume determined >30 or >90 days (respectively) after discontinuation.
- 4.9. Patient should be able to complete questionnaires (see Appendix VI), baseline questionnaires may be completed before or after enrollment, but before treatment)
 - 4.9.1. SF-12 questionnaire
 - 4.9.2. AUA questionnaire
 - 4.9.3. EPIC-26 questionnaire
 - 4.9.4. SHIM questionnaire
 - 4.9.5. Utilization of Sexual Medications/Devices questionnaire

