- 5.13. No hormone ablation for two months prior to enrollment, or during treatment. This includes LHRH agonists (e.g. leuprolide,goserelin, triptorelin) and antagonists (e.g. degarelix), peripheral blockers (e.g. flutamide, bicalutamide, nilutamide), estrogens (e.g. DES), bilateral orchiectomy, and 5-alpha reductase inhibitors (finasteride or dutasteride).
- 5.14. Completion of patient questionnaires in section 4.7.
- 5.15. Consent signed.

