- 6.2. PATIENT REGISTRATION: Patients may be registered only after all eligibility criteria are met: see Eligibility Checklist above, and Inclusion Criteria and Exclusion Criteria CRFs (Case Report Forms). After the patient signs the Consent Form the patient is enrolled in the study, and scheduled for treatment. The pre-treatment CRFs are then filled out by the investigator and/or research assistant. This data is retained in the patient's chart and in research office. The date of registration shall be the date the consent was signed. Fiducials must be placed within 60 days, and the first fraction of radiosurgery must be administered within 90 days of registrations.

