8. TREATMENT: CYBERKNIFE RADIOSURGERY

- 8.1. FIDUCIAL PLACEMENT: All patients will have gold fiducial seeds measuring 3-5 mm placed in the prostate prior to treatment planning. A minimum of three fiducial seeds will be placed under transrectal ultrasound guidance, using either transperineal or transrectal approach, with local anesthesia and/or sedation as required. The use of linked fiducials are encouraged, since they may migrate less than individually placed fiducials. The physician will place seeds such that they are visible (and not superimposed) on CyberKnife orthogonal imaging, are not collinear, and ideally are separated by 2 cm or more. Fiducials will be placed as an outpatient procedure. Local anesthestic injection, oral or intravenous sedating medication, oral or intravenous pain medication and prophylactic antibiotics may be given at the discretion of the investigator to maximize the safety and comfort of fiducial placement. At least three seeds must be usable for tracking during treatment. If an interim analysis shows unacceptable fiducial migration with a specific technique or type of fiducial, further use of this technique or type of fiducial may be prohibited by the Principal Investigator.
- 8.2. TREATMENT PLANNING IMAGING: The treatment plan will be created based on the risk group assigned by the reference lab review.
 - 8.2.1. To allow fiducial stabilization and resolution of swelling, planning studies will be imaged >= 7 days after fiducial placement. Alpha Cradle or a similar immobilization device will be used as needed.
 - 8.2.2. CT scans will be taken for treatment planning. CT slices will be 1 1.5mm, with 250-512 slices taken centered at the prostate. The imaging sets will be downloaded to the CyberKnife treatment planning system to develop the radiosurgery treatment plan.
 - 8.2.3. If not medically contraindicated, all patients will undergo MRI imaging to determine the anatomical borders of the prostate. This study will be fused to the treatment planning CT. No endorectal coil allowed.
 - 8.2.4. URETHRAL IDENTIFICATION:
 - 8.2.4.1. The planning CT and MRI scans will be done with a Foley catheter in place to define the course of the urethra through the CTV. To improve comfort and minimize inconvenience to the patient, if possible, CT and MRI planning studies will be done consecutively. The smallest possible Foley catheter will be used.

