9. PATIENT ASSESSMENTS AND TOXICITY

Assessment Preentry On tx day 4 Follow-up interval: months post therapy Years post therapy

History Physical exam (DRE) ECOG Performance Scale Prostate Biopsy & Gleason score ^a	x x x x		1 wk	1 X	3 X X X	6 X X X	12 X X X	18 X X X	24(every 6 mo up to 5 years) X ^b X ^b X ^b X	6-10
PSA	X				X	X	X	X	$\mathbf{x}^{\mathbf{b}}$	X
Prostate volume assessment Testosterone CBC, platelets BUN, creatinine	X X X X	.,	•	•	x	x	x	x	x	.,
Toxicity evaluation	X	X	X	X	X	X	X	X	$\mathbf{x}_{\mathbf{p}}$	X
AUA score	X	X	X	X	X	X	X	X	X*	X
SF-12	X			X		X	X		X*	
EPIC-26 Questionnaire	X			X		X	X		X*	X
SHIM Questionnaire	X			X		X	X		X*	X
Utilization of Sexual Rx/Devices	X			X		X	X		X*	

- a. Central review of pathology; biopsy recommended at 2 yrs, & required at time of failure
- b. Continue every 6 months through year 5
- * . Continue every 12 months through year 5.

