Appendix VI: AUA, SF-12, EPIC, SHIM, USMD Questionnaires:

American Urological Association (AUA) symptom index: was developed to help men determine how bothersome their urinary symptoms are and to check the effectiveness of treatment.⁶ This questionnaire has also been adopted worldwide and is known as the International Prostate Symptom Score (IPSS). It is sometimes seen with a Quality of Life Scale at the end of the questionnaire.

Name:	Today's date:

(Circle one number on each line)	Almost never	Less than 1 time in 5	Less than half the time	About half the time	More than half the time	Almost always
Over the past month or so, how often have you had a sensation of not emptying your bladder completely after you finished urinating?	0	1	2	3	4	5
Over the past month or so, how often have you had to urinate again less than two hours after you finished urinating?	0	1	2	3	4	5
Over the past month or so, how often have you found you stopped and started again several times when you urinated?	0	1	2	3	4	5
Over the past month or so, how often have you found it difficult to postpone urination?	0	1	2	3	4	5
Over the past month or so, how often have you had a weak urinary stream?	0	1	2	3	4	5
Over the past month or so, how often have you had to push or strain to begin urination?	0	1	2	3	4	5
	None	1 time	2 times	3 times	4 times	5 or more times
Over the past month, how many times did you most typically get up to urinate from the time you went to bed at night until the time you got up in the morning?	0	1	2	3	4	5

 Quality of Life: If you were to spend the rest of your life with your urinary condition just the way it is now, how would you feel about that? Delighted, Pleased, Mostly satisfied, Mixed, Mostly dissatisfied, Unhappy, Terrible

SF-12 (Short Form)

 In general, would you say your health is excellent, very good, good, fair, or poor? Excellent ... Very Good ... Good ... Fair ... Poor ...

The following items are about activities you might do during a typical day. Does your health now limit you in these activities? If so, how much?

- 2) First, moderate activities such as moving a table, pushing a vacuum cleaner, bowling or playing golf. Does your health now limit you a lot, limit you a little, or not limit you at all. Limited a lot ... Limited a little ... Not limited at all ...
- 3. Climbing several flights of stairs. Does your health now limit you a lot, limit you a little, or not limit you at all? Limited a lot ... Limited a little ... Not limited at all ...

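### Section 4.9 lets baseline quality-of-life forms follow fiducial placement and planning procedures, in conflict with 5.14, 6.2, 9.1.1 and the schedule; late baselines could make decline look smaller, by an unknown amount

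*Combined protocol and SAP*

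**What the plan says.** **Timing of the forms.** Section 4.9 lists five questionnaires (SF-12, AUA, EPIC-26, SHIM, and use of sexual medications or devices) and states that "baseline questionnaires may be completed before or after enrollment, but before treatment". Section 5.14 lists "Completion of patient questionnaires in section 4.7" among the eligibility criteria. Section 6.2 states that "Patients may be registered only after all eligibility criteria are met" and sets the registration date as the date of consent. In the Section 9 schedule all five forms are marked in the pre-entry column. Section 9.1.1 also calls the assessment pre-entry and, like 5.14, refers to 4.7. But 4.7 reads "CBC, platelets, serum BUN, creatinine and testosterone; may be drawn after registration"; the questionnaires are in 4.9.

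**What happens before the first fraction.** Section 6.2 states: "Fiducials must be placed within 60 days, and the first fraction of radiosurgery must be administered within 90 days of registrations". Section 8.1 requires at least three seeds, placed through the rectum or the perineum. Section 8.2.1 states that "planning studies will be imaged >= 7 days after fiducial placement" and gives resolution of swelling as one reason. Sections 8.2.4 and 8.4.2 require enemas, a Foley catheter, and draining and refilling of the bladder for the planning scans.

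**Recall periods (Appendix VI).** The AUA items begin in the style of "Over the past month or so, how often have you had a sensation of not emptying your bladder completely". Most SF-12 items and the EPIC-26 items cover 4 weeks. The SHIM covers 6 months.

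**Analysis.** Section 11.4.2 fits a straight line by GEE to each score over time and hypothesizes that the slope is not significantly below zero. It also expects early urinary and bowel worsening to return to normal, and sexual function to worsen gradually against baseline.

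**The concern.** A site that follows 4.9 may collect the baseline at the planning visit or on the first treatment day. A site that follows 5.14 and 6.2 collects it by the day of consent. The first site's forms can report symptoms from seed placement, enema and catheter as pre-treatment function. Baselines taken before and after these procedures would then be pooled according to site habit.

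If the procedures temporarily worsen scores, the bias has one direction. Mean decline from baseline shrinks, the fitted slope is less adverse, and a return to normal is easier to show. The plan relies on these scores to describe tolerability and to compare it with outside studies that used the same instruments.

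**Working it through.** The quality-of-life objective has no stated sample size, margin or effect size, so there is no figure of the plan's own to reproduce.

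**Step 1. Set the timing rules side by side.**

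| Source | Latest time for baseline forms |
|---|---|
| 5.14 with 6.2 | Registration, which is the date of consent (day 0) |
| 9.1.1 and Section 9 schedule | Before entry |
| 4.9 | Before treatment, after enrollment allowed |
| 4.7 (cited by 5.14 and 9.1.1) | Does not mention questionnaires |

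The first two rows conflict with the third, and no rule of precedence is stated. Section 4.9 also does not define treatment with respect to fiducial placement. Placement is 8.1, under the Section 8 treatment heading, so a narrow reading of 4.9 would exclude forms completed after placement. If treatment means radiosurgery, forms are allowed up to the first fraction, at most day 90.

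**Step 2. Check whether the recall period can reach the procedures.**

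- A form completed at planning imaging 7 days after placement has a 28-day recall period that includes placement, with 28 - 7 = 21 days to spare.
- If fiducials go in at the day-60 limit, the first fraction follows within 90 - 60 = 30 days. Almost any form completed in that interval recalls the placement.
- If fiducials go in early, a form completed shortly before day 90 may no longer recall the placement, but may still recall the planning catheter and enema.
- The SHIM's 6-month period dilutes a recent procedure, so it is less exposed.

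**Step 3. Size of a possible bias.** Let f be the share of men with a late baseline and d the mean temporary worsening in those men, in points. The documents give neither, so both are assumed.

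- Bias in mean change from baseline = f x d.
- Bias in the fitted 60-month change = 60 x (tbar - t0)/Sxx x f x d. This takes baseline as the month-0 point of the line, complete data, and an independence or exchangeable working correlation.

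For EPIC-26 and SF-12, visits are at 0, 1, 6, 12, 24, 36, 48 and 60 months (9.1.4):

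- tbar = 187/8 = 23.375
- Sxx = 7957 - 8 x 23.375² = 3585.875
- leverage = 23.375/3585.875 = 0.00652 per month
- over 60 months: 60 x 0.00652 = 0.39

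For the AUA, which has more visits, the same formula gives 0.21 with the 6-monthly visits of 9.1.4 and 0.22 with the 12-monthly visits of the schedule footnote.

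With an AR-type working correlation of 0.90 or 0.95 per 6 months, the factor rises to 0.94 to 0.98 for all three visit patterns. Section 11.4.2 names no working correlation.

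**Step 4. Results on assumed inputs.**

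| f | d | Change from baseline (f x d) | Fitted 5-year change, EPIC-26 (x 0.39) |
|---|---|---|---|
| 10% | 2 | 0.2 | 0.08 |
| 25% | 5 | 1.25 | 0.49 |
| 50% | 10 | 5.0 | 1.96 |
| 100% | 10 | 10 | 3.9 |

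For the AUA with d = 2 and f = 30% to 50%, f x d is 0.6 to 1.0 points. The fitted 5-year change moves by 0.6 x 0.21 = 0.13 to 1.0 x 0.22 = 0.22 points under independence, and by about 0.57 to 0.98 under the AR-type correlation. If f or d is zero, the bias is zero.

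**The case against.** **Section 4.9 may not govern.** A reader might infer that 4.9 overrides the other sections. The documents do not say so: 5.14, 6.2, 9.1.1 and the schedule all point to a pre-registration baseline, and sites may have followed them. This stands. What can be shown is a contradiction with two wrong cross-references, not a decision to take the baseline late.

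**The harm may be nil.** A reader might also infer that the plan does understate decline. The documents do not support that. The only fiducial risk listed (Section 14) is rare infection, and the 7-day wait is meant to let swelling resolve. The needle-trauma remark in 1.14 concerns brachytherapy, particularly with more than 13 insertions, against a minimum of three seeds here. This stands too: the direction is conditional and the size unknown.

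**The planned analysis is a slope.** It would be tempting to carry f x d over to every visit, or to say that every hypothesis in 11.4.2 is stated against baseline. Only the sexual-function hypothesis says so expressly, and no visit-wise change from baseline is planned. Under independence the fitted line is much less sensitive than f x d. Under an AR-type correlation it is not.

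**A late baseline can be defended.** Forms completed close to radiosurgery would isolate the effect of radiation. Earlier forms may fall nearer the diagnostic biopsy, for which 5.2.2 sets a one-year limit and no minimum gap. Either timing could be chosen, but this does not justify mixing the two by site habit.

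**An amendment may come too late.** Section 11.2 reports an interim analysis and counts 260 subjects, against 253 required, so accrual appears complete. If so, most of the value lies in the retrospective check.

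**Conclusion.** The point holds as an inconsistency with a possible bias. The sections contradict one another on when baseline questionnaires are due, and 5.14 and 9.1.1 cite the wrong section. If treatment in 4.9 means radiosurgery, the rule permits a baseline whose recall period includes fiducial placement and planning catheterization for the AUA, SF-12 and EPIC-26.

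If those procedures worsen scores temporarily, decline can be understated. The bias is share x shift for change from baseline. On the fitted 5-year change it is about 0.2 (AUA) or 0.4 (EPIC-26) of that under independence, and close to all of it under the AR-type correlations tried. These factors assume that baseline enters the line at month 0 and that data are complete. No actual bias is established. The point concerns a secondary objective; the primary bDFS and toxicity analyses are unaffected.

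**What to change.** 1. Reconcile 4.9 with 5.14, 6.2, 9.1.1 and the schedule. For any further enrollment, require all baseline questionnaires before fiducial placement.
2. Change the references to 4.7 in 5.14 and 9.1.1 to 4.9.
3. For men already enrolled, use recorded dates to flag whether each baseline form preceded fiducial placement, and report the share that did not.
4. Repeat the 11.4.2 GEE analyses excluding late baselines, and state the working correlation, because the sensitivity of the slope depends on it.

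The cost is small. Consent precedes fiducial placement, so the timing rule should need no extra visit. The AUA, EPIC-26, SHIM and device-use forms carry a completion date, and the 60-day rule in 6.2 requires the placement date to be known. The SF-12 as reproduced in Appendix VI shows no date field, so its date may have to come from the case report form. The downside is a little extra analysis and fewer men in the sensitivity analysis.
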